13.0 STATISTICAL CONSIDERATIONS

13.1 Sample Size and Power Estimates

The primary endpoint of this trial is DFS measured from study entry (time of randomization) until documented progression or death from any cause. The superiority hypothesis of celecoxib use will be tested in this patient population using the DFS endpoint. Non-exponential survival is expected. Based on the findings from NSABP C07 and the MOSAIC trials, the DFS distribution under the null hypothesis assumes probabilities of failure by year for years 1 through 6 to be 0.10, 0.12, 0.06, 0.05, 0.03 and 0.02, respectively. It is anticipated that 2,500 patients will be enrolled in 3.125 years (800 patients per year) with a follow-up period of 3 years.

The number of expected DFS events at the conclusion of the trial ($n=775$) is estimated using the method proposed by Schoenfeld. A hazard ratio of 0.79 in favor of celecoxib is assumed; this corresponds to an increase in the probability of being disease-free at 3 years from 0.72 to 0.77. With 775 events observed, this difference can be detected with power of approximately 0.91 (2-sided $\alpha=0.05$). The stratified log rank test will be used to test the primary hypothesis, with stratification on the number of lymph nodes (1-3; ≥ 4) and aspirin use (no; yes).

Overall survival (OS) measured from study entry (time of randomization) until death from any cause will be studied as a secondary endpoint.

In addition, a prospective international effort is underway to pool patient level data from multiple trials that will test the duration assumption (the IDEA trial; see [Appendix VI](#)). Our goal is for the United States Intergroup to contribute 2500 patients with stage III colon cancer to this effort. Data provided to the IDEA trial will be fully de-identified. Alliance Statistics and Data Center at Duke University will maintain the data link between the coded patient numbers provided in the de-identified dataset and the patient study ID numbers. Any interim transfer of data must be approved by the Alliance Data and Safety Monitoring Board.

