The ACCENT collaboration reported a 3-year DFS rate of 74.7% in resected stage III colon cancer patients treated since 2004 with fluorouracil, leucovorin, and oxaliplatin³²³. In a prospectively-designed, pooled analysis of six of the most recent large, randomized adjuvant chemotherapy trials conducted between 2007 and 2015, a 3-year DFS rate of 76.0% was reported in stage III patients who received 6 months of FOLFOX (IDEA).³²⁴ Both large-scale, pooled analyses showed improved 3-year DFS rates compared to the rates reported in the original NSABP C-07 and MOSAIC trials: 3-year DFS rate of 72.0%. The current trial, CALGB 80702, enrolled fewer patients with T4 tumor (14.7%) compared to the MOSAIC trial (19.0%).

As a result, it became clear that the originally planned number of events required (775) would not be achievable unless follow-up was extended by multiple more years and that future events would predominantly be deaths from non-colorectal causes. Based on the event rate observed during the most recent 12 months, the trial is projected to observe 775 DFS events between December 2021 and March 2022. To evaluate the possibilities of reporting the trial results in a timely fashion without substantially compromising power, the power calculation was updated by an independent statistician who was blinded to trial data. A reduced number of DFS events, 696, is estimated to provide power of 85% (reduced from 90%) to detect a HR of 0.79 in favor of celecoxib (3-year DFS rate from 0.75 to 0.796 at overall 2-sided $\alpha = 0.05$). This calculation accounted for the nine previously conducted interim analyses (04/2014, 09/2014, 04/2015, 11/2015, 04/2016, 07/2016, 05/2017, 10/2017, 09/2018), and neither the efficacy nor futility boundary was crossed in any of these interim analyses. At the conclusion of the trial with at least 696 DFS events, if 2-sided stratified log-rank p-value is less than 0.038, then an efficacy in favor of celecoxib can be concluded.

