6.0 STATISTICAL CONSIDERATIONS

The three clinical endpoints are adverse events (e.g., neuropathy), disease-free survival (DFS) and survival (OS). The exact definitions for these outcomes will be equivalent to those specified in the treatment protocol (CALGB/SWOG C80702). The treatment by biomarker (or genotype) interactions will be tested for the celecoxib hypothesis. If an interaction is present, relevant hypotheses will also be tested in the treatment groups of patients receiving and not receiving celecoxib. If no interaction is present, the treatment groups will be combined (celecoxib + no celecoxib) for analysis. Power estimates for specified differences in interaction are given in Table 3. Table 4 contains power estimates for DFS comparisons of biomarker and genotype within treatment group (celecoxib; no celecoxib) by marker prevalence, detectable hazard ratio and the percent of samples available. Table 5 provides power estimates for testing the prognostic value of a marker when no treatment by marker interaction is present. Table 6 illustrates detectable differences in DFS for biomarkers quantified in quartiles. Table 7 illustrates the difference detectable with the specified power for a biomarker quantified in quartiles versus a dichotomous marker; for example, Vitamin D levels measured by plasma 25(OH)D versus K-ras mutational status. Tables 8 and 9 describe the power achieved to detect the illustrated difference in Grade 3+ toxicity rates versus a biomarker quantified in quartiles. Examples are Grade 3+ neutropenia and diarrhea versus body mass index.

Table 3. Approximate power to detect the specified hazard ratio for treatment (no celecoxib; celecoxib) by biomarker interactions with 60% (n=1,500) and 80% (n=2,000) of samples obtained (2-sided $\alpha=0.1$) assuming exponential survival, a dichotomous biomarker, equal sample sizes per group, and an overall event rate of 0.31 (775/2500).

n (events)	Hazard Ratio-Interaction	Power
	1.5	
1500 (465)		0.34,0.58,0.71
2000 (620)		0.47,0.71,0.81
	1.6	
1500 (465)		0.48,0.71,0.81
2000 (620)		0.63,0.83,0.90
	1.7	
1500 (465)		0.60,0.81,0.88
2000 (620)		0.76,0.91,0.95

Moderate to large interaction hazard ratios are detectable with adequate power.

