Table 4. Power estimates for DFS comparisons of a dichotomous biomarker or genotype within treatment groups (e.g., patients receiving celecoxib) by marker prevalence, detectable hazard ratio and the percent of samples available (log rank test, 2-sided $\alpha=0.01, 0.05, 0.10$). Exponential survival, equal numbers of samples per treatment arm, and an overall event rate of 0.31 (775/2500) are assumed.

	Detectable Hazard Ratio	1.4	1.5	1.6
Marker/Genotype Prevalence	n (number of events)			
0.5				
	750 (233)	0.49,0.72,0.82	0.69,0.87,0.92	0.84,0.94,0.97
	1000 (310)	0.65,0.84,0.90	0.83,0.94,0.97	0.94,0.98,0.99
0.2				
	750 (233)	0.30,0.53,0.65	0.46,0.69,0.79	0.61,0.81,0.88
	1000 (310)	0.41,0.65,0.76	0.61,0.81,0.88	0.76,0.91,0.95
0.1				
	750 (233)	0.15,0.33,0.45	0.23,0.45,0.58	0.33,0.57,0.69
	1000 (310)	0.21,0.42,0.55	0.33,0.57,0.69	0.46,0.69,0.79

Adequate power is achieved to detect moderate to large hazard ratios for dichotomous biomarkers or genotypes with prevalence close to 50%. The power estimates at 50% prevalence are approximately correct for biomarkers or genotypes with prevalence $\geq 30\%$ and $\leq 70\%$. For biomarkers or genotypes with prevalence near 20% and, in particular, 10%, larger differences are detectable with adequate power.

Table 5. Power estimates for DFS comparisons of a dichotomous biomarker or genotype by marker prevalence for all patients, detectable hazard ratio, and the percent of samples available (log rank test, 2-sided $\alpha=0.01, 0.05, 0.10$). Exponential survival and an overall event rate of 0.31 (775/2500) are assumed.

	Detectable Hazard Ratio	1.2	1.3	1.4	1.5
Marker/Genotype Prevalence	n (number of events)				
0.5					
	1500 (465)	0.27,0.50,0.62	0.59,0.80,0.88	0.85,0.95,0.97	0.96,0.99,0.99
	2000 (620)	0.37,0.62,0.73	0.75,0.90,0.94	0.94,0.98,0.99	0.99,0.99,0.99
0.2					
	1500 (465)	0.15,0.34,0.47	0.37,0.61,0.73	0.62,0.82,0.89	0.82,0.93,0.96
	2000 (620)	0.22,0.44,0.56	0.51,0.74,0.83	0.78,0.91,0.95	0.92,0.98,0.99
0.1					
	1500 (465)	0.08,0.21,0.32	0.18,0.39,0.52	0.034,0.58,0.70	0.51,0.74,0.83
	2000 (620)	0.11,0.27,0.38	0.26,0.49,0.62	0.47,0.71,0.80	0.67,0.85,0.91

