Adequate power is achieved to detect moderate to large hazard ratios for dichotomous biomarkers or genotypes with prevalence close to 50%. The power estimates at 50% prevalence are approximately correct for biomarkers or genotypes with prevalence $\geq 30\%$ and $\leq 70\%$. For biomarkers or genotypes with prevalence near 20% and, in particular, 10%, larger differences are detectable with adequate power.

Table 6. Approximate DFS hazard ratios (maximum versus minimum hazard under “least favorable configuration”) detectable with 70%, 80%, and 90% power for comparisons of a continuous biomarker categorized by quartiles for all patients and the percent of samples available (2-sided $\alpha=0.01, 0.05, 0.10$). The chi-square non-centrality parameters (ncp) are 20.66, 16.74, 14.16, respectively, 70%, 80% and 90% power, with $\alpha=0.01$; 16.21, 12.73, 10.46, respectively, for $\alpha=0.05$; and 8.67, 10.77, and 14.02, respectively, for $\alpha=0.1$. Exponential survival and an overall event rate of 0.31 (775/2500) are assumed.

	Detectable Hazard Ratio (DFS)		
Power	0.7	0.8	0.9
n (number of events)			
1500 (465)	1.64,1.53,1.47	1.72,1.60,1.54	1.82,1.70,1.64
2000 (620)	1.54,1.45,1.40	1.60,1.50,1.45	1.68,1.58,1.53

With 60 and 80% of samples studied, adequate power is achieved to detect moderate to large hazard ratios for biomarkers categorized by quartiles.

Table 7. Difference in median DFS detectable for a continuous marker categorized by quartiles (Biomarker 1) versus a second dichotomous biomarker (Biomarker 2) with approximate powers of 0.44, 0.68, 0.78, respectively, for 2-sided $\alpha=0.01, 0.05, 0.10$, with 60% of patients submitting samples and approximate powers of 0.61, 0.81, 0.88, respectively, for $\alpha=0.01, 0.05, 0.10$, with 80% of patients submitting samples (logrank test). Exponential survival, equal sample sizes per group, and an overall event rate of 0.31 (775/2500) are assumed.

	Median DFS (years)			
Biomarker 1	Quartile(1)	Quartile(2)	Quartile(3)	Quartile(4)
Biomarker 2				
Absent	8.0	9.0	10.0	11.0
Present	9.0	8.0	7.0	6.0

Moderate to large interaction hazard ratios are detectable with adequate power.

Table 8. Power estimates to detect the difference illustrated in Table 9 for a continuous marker categorized by quartiles versus toxicity (< Grade 3+; \geq Grade 3+) for 60% (ncp=9.2) and 80% (ncp=12.3) of patients submitting samples (chi-square, 2-sided $\alpha=0.01, 0.05$).

	Significance Level	
n	$\alpha=0.01$	$\alpha=0.05$

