1500 (60% of patients)	0.67	0.85
2000 (80% of patients)	0.82	0.93

Table 9. Difference in proportions of patients by a continuous marker categorized in quartiles versus toxicity (< Grade 3+; \geq Grade 3+) that is detectable with power given in Table 8. A Grade 3+ toxicity prevalence of 0.3 is assumed.

Biomarker	Quartile(1)	Quartile(2)	Quartile(3)	Quartile(4)	Total
Adverse Event					
< Grade 3+	0.1875	0.18	0.175	0.1625	0.7
\geq Grade 3+	0.0625	0.075	0.075	0.0875	0.3
Total	0.25	0.25	0.25	0.25	1.0

For gene expression analyses, we will assume that 775 events are expected in the clinical study. This corresponds to an event rate of 0.31. We will assume that 70% will provide consent and usable samples for these analyses. The corresponding sample size and number of events to be used for the power calculations are 1750 and 542 respectively. For these simulations, we will assume that the DFS distribution is mixture of exponentials, with rates $-\log(0.72)/3$ and $-\log(0.77)/3$ respectively, and that the censoring distribution is uniform. The parameters on the latter are chosen so as to set the expected event rate is 0.31. The power, at the two-sided 0.01 FWER Bonferroni adjusted level, is illustrated in Table 10 based on a Kendall tau coefficient of 0.11, 0.12 and 0.13 under the Gaussian, Frank and Gumbel copulas. Each illustration is based on 10,000 Monte Carlo simulations. As we have pointed out, we will sharpen these FWER bounds through permutation resampling for the analyses.

Table 10. Power illustration for the gene expression study at the two-sided 0.05 FWER level

tau	Copula	Power
0.11	Normal	0.79
0.12		0.91
0.13		0.97
0.11	Frank	0.82
0.12		0.92
0.13		0.98
0.11	Gumbel	0.54
0.12		0.71
0.13		0.84

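### Appendix II still states DFS power on 775 events although amended Section 13.1 allows the trial to conclude at 696, and the Table 10 text and title give different error levels

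*Combined protocol and SAP*

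**What the plan says.** Appendix II Section 6.0 gives the power of the companion studies.

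- Table 3 (treatment-by-marker interaction) assumes exponential survival "and an overall event rate of 0.31 (775/2500"). Tables 4 and 7 state the same rate. For Tables 5 and 6: "Exponential survival and an overall event rate of 0.31 (775/2500) are assumed".
- For Table 10 (gene expression): "For gene expression analyses, we will assume that 775 events are expected in the clinical study". Taking 70% gives 1,750 patients and 542 events. The simulated DFS times come from 3-year rates of 0.72 and 0.77.
- The sentence introducing Table 10 gives a two-sided Bonferroni family-wise error rate (FWER) of 0.01. The table title gives 0.05. Appendix II Section 5.0, Objective 1.5, plans the feature test at 0.05.

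Section 13.1, as amended, says that 775 events could not be reached without several more years of follow-up, and lowers the requirement: "At the conclusion of the trial with at least 696 DFS events". The revised effect assumption is "3-year DFS rate from 0.75 to 0.796 at overall 2-sided" alpha of 0.05. It also gives a date for the old target: "the trial is projected to observe 775 DFS events between December 2021 and March 2022".

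**The concern.** One document carries two event counts for the same trial. Section 13.1 was amended and Appendix II Section 6.0 was not. The division 775/2500 = 0.31 is correct; the input is what was left behind. Companion power depends on the number of events, so a smaller count means less power at every hazard ratio in Tables 3-5, 7 and 10.

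The two error levels for Table 10 are a separate contradiction and depend on no assumption about the data cut. The same nine powers cannot hold at both 0.01 and 0.05.

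The stake is the accuracy of planning figures for secondary science. No sample size, stopping boundary or primary inference rests on these tables.

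**Working it through.** **Events.** At 696, the rate is 696/2500 = 0.2784.

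| Patients | Events at 0.31 | Events at 0.2784 |
|---|---|---|
| 1500 | 465 | 417.6 |
| 2000 | 620 | 556.8 |
| 750 | 233 | 208.8 |
| 1000 | 310 | 278.4 |
| 1750 | 542 | 487.2 |

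**Tables 3-5, plan's figures first.** Power = Φ(z − z_crit). For a marker of prevalence p, z = ln(HR)·√(D·p(1−p)). For the balanced interaction, z = ln(HR)·√(D/16). With the 775-based D, 143 of the 144 printed values are reproduced within about 1.2 points. The exception is the first value in the Table 5 cell "0.034,0.58,0.70" (prevalence 0.1, HR 1.4, n = 1500), where the formula gives 0.345; 0.034 looks like a misprint of 0.34. The Table 3 caption names only alpha = 0.1, but its three values per cell match 0.01, 0.05 and 0.10.

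**Tables 3-5 at 696.** Worked cell: Table 5, prevalence 0.5, HR 1.3, n = 1500, alpha 0.05.

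- 465 events: z = 0.2624 × √(465/4) = 2.829; Φ(2.829 − 1.960) = 0.81 (printed 0.80).
- 417.6 events: z = 0.2624 × √(417.6/4) = 2.681; Φ(0.721) = 0.76.

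Other examples at alpha 0.05: Table 3, HR 1.6, n = 2000, 0.83 to 0.79; Table 4, prevalence 0.2, HR 1.5, n = 1000, 0.81 to 0.77. The largest loss over all cells is 5.9 points at alpha 0.01, 4.7 at 0.05 and 4.1 at 0.10. At later cuts the largest loss at any alpha is 4.0 points (720 events), 2.5 (740), 1.8 (750) and 1.1 (760).

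**Table 7.** With x the log ratio of the two medians in each quartile, the non-centrality is D/16 × Σ(x − x̄)² on 3 df.

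| Samples | Non-centrality at 775 | Power, alpha 0.05 | Non-centrality at 696 | Power, alpha 0.05 |
|---|---|---|---|---|
| 60% | 8.45 | 0.68 (as printed) | 7.58 | 0.63 |
| 80% | 11.26 | 0.81 (as printed) | 10.11 | 0.77 |

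**Table 6.** With the two extreme quartiles at ±ln(HR)/2 and the others midway, non-centrality = D·(ln HR)²/8, so HR = exp√(8·ncp/D).

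- At alpha 0.01 and 0.05 the caption lists its values in reverse of the 70/80/90% labels. At alpha 0.05, n = 1500, the first value (16.21) gives HR 1.70, the table's 90% entry; the 70% entry of 1.53 needs the third value (10.46).
- The values exceed what a 3-df quartile test needs. At alpha 0.05 and 80% power the caption has 12.73; 3 df needs 10.90.
- At 696 events under 3 df, the printed HR 1.60 (n = 1500) gives 417.6 × (ln 1.60)²/8 = 11.53 and power 0.82. HR 1.50 (n = 2000) gives 11.44 and 0.82. All 12 entries at alpha 0.05 and 0.10 keep at least their stated power. At alpha 0.01 any shortfall is at most about 1 point.

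**Table 10, by simulation.** Stated inputs: n = 1750, 542 events, 3-year DFS 0.72/0.77. Assumed: K = 24,000 features (Section 5.0 gives this only as a maximum), a 50:50 mixture, a rank-based score test, and uniform censoring over an accrual-type window tuned to the event rate (Section 13.1: "It is anticipated that 2,500 patients will be enrolled in 3.125 years"); 1,500 runs per cell.

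| Copula | Printed (tau 0.11/0.12/0.13) | Simulated, 0.05 | Simulated, 0.01 |
|---|---|---|---|
| Normal | 0.79/0.91/0.97 | 0.77/0.91/0.96 | 0.67/0.84/0.92 |
| Frank | 0.82/0.92/0.98 | 0.81/0.91/0.97 | 0.70/0.85/0.94 |
| Gumbel | 0.54/0.71/0.84 | 0.52/0.68/0.82 | 0.39/0.56/0.72 |

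With censoring uniform from zero the fit is worse, but 0.05 is still closer (Normal 0.71/0.85/0.94 against 0.60/0.76/0.89). At 0.05 with 487 events and 0.75/0.796, accrual-type censoring gives Normal 0.74/0.87/0.95.

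**The case against.** The best defence is that 775 is an openly declared planning assumption, not a miscalculation. Tables 3-6 print the event count beside each row, so Tables 3-5 remain right at those counts, apart from the one misprint. Only the link to sample availability moves: 465 and 620 events would need 67% and 89% of patients instead of 60% and 80%. Availability is itself a guess, and its effect on power (Table 7: 0.68 against 0.81) exceeds the loss found here. This stands, and it is why the consequence is low.

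Three stronger readings are tempting and are not supported.

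- *That the companion studies will fall short of the stated power.* 696 is a minimum, Appendix II sets no data cut-off, and Section 13.1 projects a date range for 775 events. The loss is conditional on the cut. Counting the cells that drop below 0.80 adds little: of 59 values printed at 0.80 or more, the count at 696 events is 13 or 15 depending on rounding, and Appendix II sets no such threshold.
- *That the Table 6 hazard ratios must rise, for example from 1.60 to 1.64.* That carries forward the oversized non-centrality values. On 3 df the printed ratios keep about their stated power.
- *That 0.01 in the Table 10 text is certainly the error.* K and the censoring limits are not given. K of about 4,800 at 0.01 has the same per-test level as 24,000 at 0.05 (both about 2.1 × 10⁻⁶).

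**Conclusion.** The point holds, with low consequence. The powers in Tables 3-5, 7 and 10 rest on an event count that the amended design need not reach, and Table 10 also rests on superseded DFS rates. At a 696-event cut the overstatement is at most 5.9 points in Tables 3-5 (4.7 at alpha 0.05) and about 4 to 5 points in Table 7 at alpha 0.05. It disappears if the companion analyses wait for 775 events. The statements that moderate to large hazard ratios are detectable survive.

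The two error levels for Table 10 conflict on the face of the text. That 0.05 is the level behind the printed powers is probable, given K near 24,000, but not proven. Table 6 needs its non-centrality values corrected, but not because of the event count.

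**What to change.** 1. State in Appendix II the event count or data cut intended for the companion analyses.
2. Restate Tables 3-5 and 7 at that count. If it is 696, use 418 and 557 events pooled and 209 and 278 within arm.
3. Rerun Table 10 at 0.05 FWER with K and the censoring limits stated, and give that level in both text and title. If the count is 696, use 487 events and 3-year DFS of 0.75/0.796.
4. Recompute Table 6 with 3-df non-centrality values listed in the order of the power labels.
5. In the same pass, correct 0.034 to 0.34 in Table 5 and the Table 3 caption to alpha = 0.01, 0.05, 0.10.

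The cost is recalculation only. At a 696-event cut, stated powers in Tables 3-5, 7 and 10 become slightly lower. In Table 6 the 80%-power hazard ratios at alpha 0.05 become about 1.58 and 1.49 in place of 1.60 and 1.50.

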APPENDIX II**CORRELATIVE SCIENCE COMPANION STUDIES: CALGB 150911****1.0 OBJECTIVES**

- 1.1 To assess molecular features within the tumor that influence the efficacy of celecoxib as adjuvant therapy for stage III colon cancer.
- 1.2 To assess whether markers of systemic inflammation in blood can predict the efficacy of celecoxib as adjuvant therapy for stage III colon cancer.
- 1.3 To assess the influence of baseline plasma 25(OH)-vitamin D level on disease-free and overall survival in patients with stage III colon cancer.
- 1.4 To assess whether tumoral expression of vitamin D receptor (VDR) and 1- α -hydroxylase and KRAS mutational status modifies the relation between baseline plasma 25(OH)-vitamin D level on patient outcome.
- 1.5 To determine an mRNA expression signature that is predictive of disease-free survival among patients with stage III colon cancer
- 1.6 To determine an mRNA expression signature that predicts efficacy of celecoxib as adjuvant therapy for patients with stage III colon cancer
- 1.7 To determine if CpG island methylator phenotype (CIMP) is an independent predictor of DFS in patients with stage III colon cancer
- 1.8 To determine the association between cytotoxic and memory T cell infiltration and density of immunosuppressive M2 macrophages and survival outcomes in stage III colon cancer and whether the associations are stronger for patient treated with celecoxib who have increased cytotoxic and memory T cell infiltration and lower M2 macrophase density.
- 1.9 To perform whole-genome sequencing of paired tumor/normal DNA and methylation-sequencing of tumor DNA and obtain a more complete characterization of CRC.
- 1.10 To conduct a metagenomic and 16S RNA analyses of tumor-colonizing bacteria in FFPE primary tumors.

2.0 BACKGROUND**2.1 Tumoral molecular alterations associated with the efficacy of COX-2 inhibition**

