with prior studies. In secondary analyses, we will examine how the relationship between 25(OH)D level and patient outcome is modified by relevant covariates such as ECOG performance status, treatment assignment, physical activity and body mass index, among others. Tests for statistical interaction will be performed by entering into the model the cross-product term of the plasma 25(OH)D as a continuous variable with the covariate as a continuous or binary variable.

For the analysis of tumoral alterations in vitamin D and related pathways (**Objective 1.4**), all patients who had a tumor block available for analysis of VDR expression, 1- α -hydroxylase, and KRAS mutation and data on circulating 25(OH)D concentration will be included. Tumoral protein overexpression will be defined as a) moderate/strong staining in any fraction of cells, or b) $\geq 50\%$ of tumor cells with weak staining. All tumors will be categorized as having VDR and 1- α -hydroxylase overexpression versus no overexpression, and KRAS mutated versus wild type. Within each of category of VDR expression, 1- α -hydroxylase expression, and KRAS mutational status, we will examine the influence of plasma levels of 25(OH)D divided into tertiles on DFS and OS. Tertiles will be utilized instead of quintiles of plasma 25(OH)D to maximize the ability to detect an association within each subgroup. Cox proportional hazards models will be used to calculate HRs and 95% CIs for DFS and OS, adjusted for other prognostic factors. Tests for statistical interaction will be performed by entering into the model the cross-product term of plasma 25(OH)D as a continuous variable with the molecular alteration as a binary variable (overexpressed versus not; mutated versus wild type).

In describing analyses related to gene expression, the genes/transcripts from RNA-seq will be referred to as features. The terms feature, feature expression and expression will also be used interchangeably. The maximum number of features is approximately 24,000. In these discussions, K will denote the number features (among the 24,000) which pass the non-phenotypic filters. The expressions, which are summary measures, are obtained following pre-processing. The background correction algorithm implemented by the BeadStudio software will be employed and quantile normalization will be applied to the background adjusted intensities.

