A molecular classification model will be constructed using conditional inference trees with binary splits.³⁸ These trees will allow for direct incorporation of the censoring mechanism, which is important given that the length of follow-up varies among patients, as well as adjustment for multiplicity. The overall error rate will be adjusted at the 0.2 level using permutation resampling. The terminal nodes of these trees will be considered "risk" groups (classified by the trees). Kaplan-Meier estimates of the hazard profiles for these risk groups will be produced and presented graphically. We will also consider the random forests for survival data.³⁹⁻⁴¹ One of the key advantages of the two methods is that they implicitly incorporate interactions among the variables.

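### No validation is planned for the expression tree's risk groups, so Kaplan-Meier curves drawn in the tree-building patients would overstate DFS separation by an amount that depends on the unknown signal

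*Combined protocol and SAP*

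**What the plan says.** The classifier is described in the last paragraph of Appendix II, section 6.0:

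- Method: "A molecular classification model will be constructed using conditional inference trees with binary splits".
- Error control: "The overall error rate will be adjusted at the 0.2 level using permutation resampling".
- Groups: "The terminal nodes of these trees will be considered" the risk groups.
- Display: "Kaplan-Meier estimates of the hazard profiles for these risk groups will be produced and presented graphically".
- Second learner: "We will also consider the random forests for survival data".

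The inputs are nearby. Section 5.0 says of the expression data that "The maximum number of features is approximately 24,000". Section 6.0 says "We will assume that 70% will provide consent and usable samples for these analyses", and gives 1,750 patients and 542 events for the gene expression power calculation. Table 10 gives power for a single feature with Kendall tau of 0.11, 0.12 or 0.13.

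The aim served is Objective 1.5: "To determine an mRNA expression signature that is predictive of disease-free survival among patients with stage III colon cancer". Hypothesis 3.5 in section 3.0 repeats it.

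The plan does not say which patients the curves are drawn in. Neither section 5.0 nor section 6.0 describes a step that estimates how the groups separate in patients not used to build the tree.

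**The concern.** At each split the tree picks, from up to about 24,000 features, the one most associated with DFS, and then the cut-point that separates the patients best. Outcome differences between the resulting nodes are therefore partly real and partly the luck that got that feature and cut-point chosen. Curves in the same patients show both parts; new patients would show only the real part.

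The control at 0.2 acts on whether a split is made. Once a split has been accepted, nothing shrinks the separation that is displayed.

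A signature that predicts DFS is a claim about future patients. Without an estimate in patients outside the building set, the only evidence on prediction would be a figure biased in the favourable direction.

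**Working it through.** **1. The plan's own figures.** 775/2,500 = 0.31; 2,500 × 0.70 = 1,750; 1,750 × 0.31 = 542.5. The stated 1,750 patients and 542 events reproduce. The plan states no separation, hazard ratio or C-index for the risk groups, so there is no figure of that kind to reproduce.

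**2. Is any patient set reserved?** The power calculation for feature discovery uses all 1,750. No second expression cohort, training/test split or resampling estimate is described for this classifier. The quality and stability checks elsewhere in Appendix II concern assays, raters and the immune spatial clustering, not this tree.

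**3. Simulation of the bias.** Inputs from the plan:
- n = 1,750 and 24,000 features;
- DFS as a mixture of exponentials with rates -log(0.72)/3 and -log(0.77)/3;
- uniform censoring set to give 31% events;
- error level 0.2, and Table 10's tau values, converted to a Gaussian correlation by r = sin(π·tau/2), so tau 0.12 gives r = 0.187.

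Assumptions not in the plan:
- independent Gaussian features and a Gaussian copula;
- 0.2 applied at each node with a Sidak adjustment, 1 - (1 - p)^24,000 < 0.2, that is p below about 0.2231/24,000 = 9.3 × 10⁻⁶;
- log-rank scores, with the cut-point at the largest two-sample statistic;
- minimum node of 7 patients (88 in sensitivity runs).

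Each scenario had 60 to 80 replicates. For the highest- and lowest-risk nodes, the apparent HR is the ratio of event rates (events/person-time) in the building patients. The real HR is the same ratio for the same nodes in 30,000 to 40,000 new patients. The ratio reported is mean log apparent HR divided by mean log real HR, given at least one split. For tau 0.11: ln 2.01/ln 1.39 = 0.698/0.329 = 2.1.

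| True signal | Apparent HR | Real HR | Log-HR ratio | 3-year DFS difference in points, apparent vs real |
|---|---|---|---|---|
| 1 feature, tau 0.11 | 2.01 | 1.39 | 2.1 | 15.2 vs 8.0 |
| 1 feature, tau 0.12, run 1 | 2.18 | 1.49 | 1.9 | 17.5 vs 9.6 |
| 1 feature, tau 0.12, run 2 | 2.32 | 1.46 | 2.2 | 18.2 vs 9.0 |
| 1 feature, tau 0.13 | 2.11 | 1.55 | 1.7 | 17.6 vs 10.5 |
| 1 feature, tau 0.20 | 3.43 | 2.14 | 1.6 | 27.3 vs 17.9 |
| 1 feature, tau 0.30 | 8.26 | 5.43 | 1.25 | 48.8 vs 39.9 |
| 5 features, tau 0.12 | 4.19 | 1.83 | 2.4 | 31.7 vs 14.7 |
| 10 features, tau 0.08 | 2.74 | 1.37 | 3.2 | 22.1 vs 7.6 |
| 10 features, tau 0.06 | 1.86 | 1.18 | 3.7 | 14.5 vs 4.0 |
| 30 features, tau 0.06 | 2.33 | 1.21 | 4.4 | 19.1 vs 4.7 |
| 1 feature, tau 0.08 | 2.21 | 1.19 | 4.5 | 14.2 vs 4.1 |
| 50 features, tau 0.04 | 2.00 | 1.10 | 7.5 | 14.9 vs 2.4 |

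The ratios come from unrounded means, so recomputing from the rounded HRs can differ slightly. The two runs at tau 0.12 indicate the Monte Carlo noise, about 0.3. With nodes of at least 88 patients the ratio is 2.0 at tau 0.12 and 1.4 at tau 0.20.

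**4. No signal.** A tree still splits in about 18% of runs, as a 0.2 level allows. It then shows an apparent HR of about 1.9 when the real one is 1.0. The ratio has no finite value there.

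**The case against.** **The patient set is not named.** This stands. Use of the building patients is inferred from the absence of any other set, so the conclusion has to be conditional.

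**No single inflation factor can be given.** This also stands. A reader might infer that the curves will show some fixed multiple of the real separation, say two to three times. The documents give no such figure, and the simulated ratio runs from 1.25 to more than 7 with the true signal.

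**The formal analyses do not use the curves.** Section 5.0 tests each feature for Objective 1.5 by a rank-covariance measure with permutation P-values at a family-wise 0.05 level. Objective 1.6, on who benefits from celecoxib, uses Cox interaction models. A reader might infer that the gene discovery or the celecoxib-benefit signature is biased too. The documents do not support that, since neither analysis passes through the tree. The plan also promises no hazard ratio or C-index for the nodes. But a list of significant features does not show how well a signature predicts, and the tree is the planned step that turns features into risk groups.

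**Cross-validation assesses the procedure, not the final tree.** This is correct: trees differ between folds and their nodes cannot be matched. It shapes the remedy without removing the need for one.

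**This is an optional companion study.** That is true, and it limits the severity. It does not make a biased display of a predictive signature preferable to an unbiased one.

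**Conclusion.** The point holds in conditional form. The plan defines risk groups by the fitted tree and plots them, with no estimate of their separation outside the building data. If the curves are drawn in the building patients, which is the natural reading, DFS separation will be overstated. The log-HR ratio is about 1.7 to 2.2 for one Gaussian feature at the Table 10 effects, about 1.25 to 1.6 for stronger single features, and about 2.4 to more than 7 for several or weak features. These sizes rest on independent features and on 0.2 applied at each node; correlated expression data would change them.

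The affected aim is Objective 1.5. Section 5.0 extends tree and forest models to adverse events, again without a validation step. The primary celecoxib comparison, the family-wise controlled feature discovery and the Objective 1.6 interaction models are untouched. The change is worth making because it is cheap, but the trial's main conclusion does not depend on it.

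**What to change.** Add to the classifier paragraph of Appendix II, section 6.0, in substance:

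- Any reported risk-group separation (curves, and any hazard ratio or C-index) will come from cross-validation, with all feature selection and splitting repeated within each training fold. Each patient is classified by a tree that did not use that patient. Because trees differ between folds, patients are pooled by predicted-risk category, with the categories fixed in advance.
- A bootstrap optimism correction or a held-out set is an acceptable alternative; the plan should name which will be used.
- Random forest performance will be based on out-of-bag predictions.
- Curves drawn in the building patients, if shown, will be labelled as descriptive.

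The same wording should cover the tree and forest models for adverse events in section 5.0.

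The cost is a few sentences of plan text and more computing, for which section 7.0 already describes substantial capacity. No further patients, samples or assays are needed. The downside is that the reported separation will look smaller. A held-out set would also reduce the number of patients available to build the tree.
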